SPIDER Study Protocol

Study Title

SPIDER – *Spinal Dural Arteriovenous Fistula International Data and Outcomes Registry*

Principal Investigator

[name], FAANS, FACS, FAHA

The [name] Distinguished Professor of Neurological Surgery and Radiology

Division Chief of Neurovascular Surgery & Endovascular Neurosurgery

Thomas Jefferson University Hospital

Study Coordinator / Contact

[name] [name]

Research Fellow, Department of Neurosurgery

Thomas Jefferson University Hospital

Study Version and Date

Version 1.0 – 20 December 2025

Background and Rationale

Spinal dural arteriovenous fistulas (SDAVFs, type I spinal vascular malformations) are the most common spinal vascular malformation but remain frequently underdiagnosed due to their insidious onset and nonspecific clinical presentation. Delayed diagnosis is common and often results in progressive, and sometimes irreversible, myelopathy. Despite advances in imaging and treatment, there remains significant variability in diagnostic timelines, treatment strategies (endovascular, surgical, or combined), and reported outcomes across institutions.

Existing literature is largely limited to single-center retrospective series or small cohorts, often underpowered to evaluate predictors of outcome, recurrence, and the impact of diagnostic delay. Furthermore, direct comparisons between treatment modalities and long-term functional outcomes using standardized clinical scales are limited.

The SPIDER registry is designed to address these gaps by creating the largest international, multicenter dataset of patients with spinal dural AVFs. By pooling de-identified data from high-volume centers worldwide, this study aims to provide robust, generalizable evidence to inform clinical decision-making and optimize patient outcomes.

Study Objectives

Primary Objectives

1. To characterize the clinical, radiological, and angiographic presentation of spinal dural AVFs.
2. To compare treatment strategies (endovascular, surgical, combined, or conservative management) and their angiographic and clinical outcomes.
3. To evaluate long-term neurological and functional outcomes following treatment.
4. To assess the impact of diagnostic delay on neurological status and long-term outcomes.

Secondary Objectives

- To identify factors associated with treatment failure or recurrence.
- To evaluate complication rates associated with different treatment modalities.
- To explore predictors of functional recovery using standardized outcome measures.

Study Design

This is an **international, multicenter, retrospective observational cohort study**.

Participating centers will contribute de-identified data on patients diagnosed with spinal dural arteriovenous fistulas who were evaluated and/or treated at their institution.

No interventions will be performed as part of this study. All data are derived from existing medical records, imaging, and procedural reports.

Study Population

Inclusion Criteria

- Patients of any age diagnosed with **spinal dural arteriovenous fistula (Type I)**.
- Diagnosis confirmed by spinal angiography, MRI findings consistent with SDAVF, and/or operative findings.
- Patients managed with endovascular treatment, open surgery, combined approaches, or conservative management.
- Both symptomatic and incidental/asymptomatic cases.

Exclusion Criteria

- Intramedullary spinal vascular malformations (e.g., glomus AVMs, juvenile AVMs).
- Perimedullary AVFs or other non-dural spinal vascular lesions.
- Cases lacking sufficient data to confirm diagnosis or treatment details.

Data Collection and Variables

Each participating center will extract data using a standardized spreadsheet with predefined categorical options to ensure consistency across sites. All data will be fully de-identified prior to submission.

Demographics and Center Information

- Country

- Study center (institution name)
- Patient study number
- Age at diagnosis
- Sex

Clinical History and Presentation

- Months from symptom onset to diagnosis
- Misdiagnoses prior to SDAVF diagnosis
- History of spinal trauma
- Incidental/asymptomatic presentation
- Presentation with rupture (spinal, intracranial, both, or none)
- Presence of myelopathy at diagnosis
- Presenting symptoms: back pain, radicular pain, sensory symptoms, motor weakness, spasticity

Functional Status at Diagnosis

- Modified Aminoff–Logue Scale (Gait)
- Modified Aminoff–Logue Scale (Bladder)
- Modified Rankin Scale (mRS)

Radiological and Angiographic Characteristics

- Laterality of fistula
- Spinal level of fistula (highest level if multilevel)
- Number of arterial feeders
- Highest and lowest arterial feeder levels (if multiple)
- Involvement of the artery of Adamkiewicz
- MRI findings (myelomalacia, cord edema, or T2 hyperintensity)

Treatment Details

- Year of treatment
- Time from diagnosis to first treatment
- Initial treatment modality:
 - Endovascular embolization alone
 - Open surgery alone
 - Combined approaches
 - Conservative management
- Endovascular details:

- Number of embolization attempts
- Embolic agent used
- Angiographic outcome
- Intra- or postprocedural complications
- Surgical details:
 - Intraoperative visualization modality
 - Indication for visualization
 - Surgical outcome (successful or unsuccessful disconnection)
 - Intra- or postoperative complications

Recurrence and Re-treatment

- Occurrence of recurrence
- Time to recurrence
- Treatment modality for recurrence
- Angiographic outcome after re-treatment

Follow-Up and Outcomes

- Duration of follow-up
- Symptom evolution at last follow-up (pain, sensory, motor)
- Modified Aminoff–Logue Scale (Gait and Bladder) at last follow-up
- Modified Rankin Scale at last follow-up
- Overall clinical status at last follow-up (improved, unchanged, worsened)
- Death, if applicable

Notes

- Additional relevant clinical or radiological comments

Outcomes

Primary Outcomes

- Functional outcome at last follow-up as measured by mRS and Modified Aminoff–Logue scales.
- Angiographic success (complete vs partial vs unsuccessful occlusion).

Secondary Outcomes

- Rate and predictors of recurrence.
- Complication rates by treatment modality.
- Association between diagnostic delay and neurological outcome.

Statistical Analysis Plan

Descriptive statistics will be used to summarize demographic, clinical, radiological, and treatment characteristics. Continuous variables will be reported as means with standard deviations or medians with interquartile ranges, as appropriate. Categorical variables will be reported as frequencies and percentages.

Comparative analyses will be performed to evaluate outcomes across treatment modalities using appropriate statistical tests (e.g., chi-square, t-test, ANOVA, or non-parametric equivalents). Multivariable regression models may be used to identify independent predictors of outcomes and recurrence.

Missing data will be handled using appropriate statistical methods depending on the extent and pattern of missingness.

Ethical Considerations

This study involves retrospective collection of **fully de-identified data** and poses minimal risk to participants. No direct patient contact will occur, and no protected health information will be shared.

Each participating institution is responsible for obtaining local Institutional Review Board (IRB) or Ethics Committee approval or exemption, as required by local regulations.

Data will be securely stored and accessed only by authorized study investigators.

Data Sharing and Publication Policy

Contributing centers will retain ownership of their local data. Aggregated data will be used for pooled analyses, conducted at the main study center. All participating centers will have

the opportunity to submit project proposals to conduct analyses using the study database, subject to review and approval at the discretion of the main study center.

Authorship on resulting manuscripts will follow ICMJE guidelines and will include contributors from participating centers based on data contribution and intellectual involvement.

If enrollment targets are met, the SPIDER registry is expected to support multiple high-impact publications addressing clinical presentation, treatment strategies, radiological predictors, and outcomes.

Timeline

- Center enrollment and IRB approvals: Ongoing
- Data collection deadline: **End of February 2026**
- Data cleaning and analysis: 2026
- Manuscripts preparation and submission: 2026

Funding and Conflicts of Interest

This study is investigator-initiated and currently unfunded. Any potential conflicts of interest will be disclosed in resulting publications.

Conclusion

The SPIDER registry aims to establish the most comprehensive international dataset on spinal dural AVFs to date. By leveraging multicenter collaboration, this study seeks to generate high-quality evidence to improve diagnosis, treatment selection, and long-term outcomes for patients with this rare but debilitating condition.

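### MRI alone can confirm the diagnosis and no variable records the basis of confirmation, so any misclassification would fall mainly in the conservative group and could not be reliably checked

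*Protocol*

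**What the plan says.** Under Study Population, the Inclusion Criteria require "Diagnosis confirmed by spinal angiography, MRI findings consistent with SDAVF, and/or operative findings". They also require a diagnosis of type I spinal dural fistula, and they admit "Patients managed with endovascular treatment, open surgery, combined approaches, or conservative management".

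The Exclusion Criteria remove intramedullary malformations, "Perimedullary AVFs or other non-dural spinal vascular lesions", and "Cases lacking sufficient data to confirm diagnosis or treatment details".

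Under Data Collection and Variables, the radiological and angiographic list covers laterality, fistula level, the number and levels of arterial feeders, "Involvement of the artery of Adamkiewicz", and one MRI item, "MRI findings (myelomalacia, cord edema, or T2 hyperintensity". Initial treatment modality is recorded, and there is a free-text Notes field. No item states whether the diagnosis rested on angiography, operation or MRI.

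Primary objective 2 is "To compare treatment strategies (endovascular, surgical, combined, or conservative management) and their angiographic and clinical outcomes". The Statistical Analysis Plan section proposes tests across modalities and does not restrict them by how the diagnosis was established.

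**The concern.** Eligibility turns on where the shunt lies: dural lesions are in, perimedullary, intramedullary and other non-dural lesions are out. The confirmation rule lets the weakest of three kinds of evidence stand by itself, and the spreadsheet does not say which kind was used.

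If that weaker evidence were spread evenly over the treatment groups, the result would be some dilution everywhere. Here it is likely to gather in one group. The conservative group's presentation and outcomes could then partly describe a different disease, and so could its contrast with the treated groups. A larger registry would not remove such an error. The angiographic descriptors would also tend to be missing, or inferred, in that same group.

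**Working it through.** The Protocol states no sample size, group size or MRI-only share, so there is no figure of its own to reproduce. The check is to set the sections side by side.

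1. **Does MRI alone qualify?** Yes. The three kinds of evidence are joined by and/or, so any one suffices.

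2. **Does the insufficient-data exclusion remove MRI-only cases?** Not as a class. The inclusion rule already counts a consistent MRI as confirmation. The exclusion can still remove a case whose MRI leaves the lesion type in doubt.

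3. **Which groups can contain MRI-only cases?** This is a deduction from what the treatments involve; the Protocol does not state it.
   - Embolisation: angiography is part of the procedure.
   - Open surgery: operative findings exist.
   - Combined: both exist.
   - Conservative: neither is guaranteed.

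   MRI-only cases are therefore left mainly in the conservative group. It does not follow that most conservative cases are MRI-only, since some will have had angiography.

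4. **Can they be identified afterwards?** Only roughly. Treatment modality reveals the basis for treated cases. For conservative cases, blank feeder and Adamkiewicz fields are a hint, but a blank may also mean a poor record. Notes are not systematic. The MRI item lists cord changes and does not record the site of the shunt.

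5. **How large could the effect be?** Illustration only; every input is an assumption. Let m be the MRI-only share of the conservative group, f the share of those that are non-dural, and d the absolute difference in outcome rate between non-dural and true dural cases.
   - Non-dural share of the group = m × f
   - Shift in the group's outcome rate = m × f × d

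| m | f | m × f | shift, d = 0.2 | shift, d = 0.4 |
|---|---|---|---|---|
| 0.1 | 0.05 | 0.5% | 0.1 points | 0.2 points |
| 0.3 | 0.10 | 3% | 0.6 points | 1.2 points |
| 0.5 | 0.20 | 10% | 2.0 points | 4.0 points |
| 0.8 | 0.30 | 24% | 4.8 points | 9.6 points |

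The corresponding shift in the treated groups is about zero by step 3. The spread, from 0.1 to 9.6 points, shows that the Protocol cannot say whether the problem is negligible or material.

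**The case against.** The strongest reply is that a broad case definition is a legitimate choice for a registry of a rare disease, and that MRI is only one part of the entry rule. The patient must also carry a type I diagnosis, non-dural lesions are excluded outright, doubtful cases can be dropped, and the Protocol describes its contributors as high-volume centres. A confirmed-case population or sensitivity analysis could also be set out in a separate analysis plan that is not at hand.

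Much of this stands, and it rules out several stronger readings that a reader might infer:

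- **That an MRI-based rule cannot enforce the exclusions.** This depends on how well MRI separates dural from perimedullary shunts, which the Protocol does not discuss. The recorded cord changes are a descriptor; nothing says that they are the diagnostic definition.
- **That MRI-only cases can never be separated.** Modality together with blank feeder fields gives an imperfect flag.
- **That a particular percentage of the conservative group has the wrong disease.** No document figure supports any such number.
- **That the rule causes the gap in the primary outcome "Angiographic success (complete vs partial vs unsuccessful occlusion".** That outcome grades the result of treatment. An untreated patient has no occlusion attempt to grade, whatever the basis of diagnosis.
- **That every comparison must be limited to confirmed cases.** That would keep only those conservative patients who had angiography, a selected subgroup. It trades one bias for another.

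What the reply does not answer is the missing variable. An analysis plan can define a confirmed-case population only if the basis of diagnosis was collected, and the Protocol fixes the variable list. Comparisons among the treated groups are not affected.

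**Conclusion.** The point holds in a limited form. MRI alone counts as confirmation, eligibility depends on a dural shunt, and no collected variable records the basis of diagnosis. Any MRI-only misclassification would fall mainly in the conservative group, would be differential in the primary objective 2 comparison, and could not be reliably checked from the data.

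The conclusion rests on the plain reading of and/or, on the variable list as printed, and on the deduction that treated patients have angiographic or operative evidence. The size is unknown. The assumed range of 0.5% to 24% of the conservative group shows only how wide the uncertainty is. The change is worth making because it is cheap and cannot easily be made after data collection closes.

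**What to change.** - Add one column, basis of diagnosis, with predefined options: catheter angiography, operative findings, MRI or MRA only.
- Show MRI-only cases separately in the descriptive tables.
- Base the angiographic descriptors on cases with angiographic or operative findings.
- Keep the comparisons involving the conservative group in all eligible cases, and repeat them in confirmed cases only as a sensitivity analysis.

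**Cost.** Centres that have already extracted their data must go back and complete one more field before the deadline at the end of February 2026. The confirmed-only conservative group will be smaller and selected towards patients who underwent angiography, so its results should be read beside the full-group results and not in place of them. No patient leaves the registry.

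### Patients treated elsewhere before reaching a centre are eligible and not identifiable, so the treatment results are open to selection on the outcome, of unknown size and direction

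*Protocol*

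**What the plan says.** Under Study Design, centres contribute patients "who were evaluated and/or treated at their institution". This is the operative eligibility text: contact with the centre is enough, and the first treatment need not have been given there. The Inclusion Criteria then accept "Patients managed with endovascular treatment, open surgery, combined approaches, or conservative management". Of the three Exclusion Criteria, two concern lesion type and the third removes "Cases lacking sufficient data to confirm diagnosis or treatment details". None concerns earlier or outside treatment.

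Under Data Collection and Variables, Treatment Details lists "Time from diagnosis to first treatment" and "Initial treatment modality", the latter without saying whether it means first ever or first at the contributing centre. Recurrence and Re-treatment lists "Occurrence of recurrence", with time to recurrence, re-treatment modality and the angiographic result. No listed field records where a treatment was given or whether the patient arrived already treated. A free-text Notes field is the only place this could appear.

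The affected results are Primary Objective 2 (comparison of treatment strategies), the secondary objective "To identify factors associated with treatment failure or recurrence", the complication rates by modality, the primary outcome of angiographic success, and the secondary outcome of recurrence.

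**The concern.** Entry can depend on the result of the first treatment. A patient whose outside treatment failed or recurred has a reason to be seen at a participating centre, whereas one treated successfully outside has less. The first can enter the numerator while the second never enters the denominator. This is separate from duplicate entry, because it arises even when every patient appears exactly once.

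Because the initial modality is undefined, sites may also code the same patient differently, so the distortion need not fall on the same group at every site. If it differs between modalities, it appears as a treatment difference. The listed variables contain nothing on which an analysis could restrict, stratify or adjust.

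**Working it through.** **Is there a figure to reproduce?** No. The protocol states no sample size, failure rate, recurrence rate or referral share. The check therefore reads the text for whether the route exists, then illustrates its size on assumed inputs.

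**Step 1: follow one patient through the fields.** Take a patient embolised at a non-participating hospital, unsuccessfully, and then operated on at a SPIDER centre. The patient is eligible under Study Design and is not excluded if the records are adequate. Three codings are possible:

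- *First ever:* initial modality is endovascular, with an unsuccessful or recurrent result. The endovascular group gains a certain failure without the outside hospital's successes.
- *First at this centre:* initial modality is open surgery alone. A previously failed case counts as first-line surgery.
- *Combined approaches:* the patient sits in neither single-modality group.

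Under none of these does a structured field show that the patient arrived already treated. The recurrence field cannot separate a recurrence seen in the centre's own follow-up from one that prompted the referral.

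**Step 2: effect on one rate (assumed inputs).** Suppose 100 in-house cases with a true failure rate of 20%, plus r referred-in failures coded to the same modality. The observed rate is (20 + r)/(100 + r).

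- r = 5: 25/105 = 23.8%
- r = 10: 30/110 = 27.3%
- r = 15: 35/115 = 30.4%
- r = 20: 40/120 = 33.3%

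Equivalently, if a share f of a group's records are outside failures and p is the true rate, the observed rate is (1 − f)p + f. With p = 10%, f of 2%, 5%, 10% and 20% gives 11.8%, 14.5%, 19.0% and 28.0%. With p = 20%, the same shares give 21.6%, 24.0%, 28.0% and 36.0%.

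**Step 3: effect on a comparison (assumed inputs).** Give two modalities the same true rate but different shares f, and apply a two-sided 5% test of two proportions. The last column is the chance of a spurious significant difference with 100, 200 and 400 patients per group.

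| True p | f in each group | Observed rates | Odds ratio | Chance of p < 0.05 |
|---|---|---|---|---|
| 10% | 10% vs 2% | 19.0% vs 11.8% | 1.75 | 29%, 51%, 81% |
| 10% | 10% vs 5% | 19.0% vs 14.5% | 1.38 | 13%, 22%, 40% |
| 20% | 10% vs 2% | 28.0% vs 21.6% | 1.41 | 18%, 32%, 55% |

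For the first row, the odds ratio is (0.19/0.81)/(0.118/0.882) = 1.75. A larger registry makes the false signal more likely to reach significance.

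**Step 4: with the flag.** Restricting to patients with no earlier outside treatment sets f to 0, and the formula returns p.

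**The case against.** A reader might infer that the endovascular and surgical groups *are* enriched with failures, or that the plan is biased against one modality. The documents do not support either. The Background says only "By pooling de-identified data from high-volume centers worldwide"; that such centres receive failed cases is plausible but not stated, and no referral share is given. Direction is also open. Patients merely evaluated at a centre are eligible, so some outside successes may enter, and in-house failures re-treated elsewhere may go unrecorded and lower the observed rate. The illustrations make every referred-in case a failure and let no outside success in, so they show the mechanism and do not estimate the bias.

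Other points carry some weight:

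- *Insufficient data is an exclusion.* This will remove some thinly documented outside cases, but well-documented failures still enter.
- *The layout suggests first-ever treatment.* Timing runs from diagnosis to first treatment, and recurrence has its own block. That makes coding the example patient as first-line surgery less natural. It leaves the first-ever coding, under which the failed modality gains certain failures.
- *The spreadsheet and any SAP are not shown.* Either may hold coding rules. But the protocol's variable list is detailed and has no such field, and an SAP cannot restrict on a variable that was not collected.
- *Sites can be queried during data cleaning in 2026.* True, so the problem can be repaired. Such a query would amount to collecting the missing field late.

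**Conclusion.** The concern holds as a matter of exposure. As written, the protocol admits patients who reach a centre because an earlier outside treatment failed or recurred, does not identify them in any listed structured field, and leaves initial treatment undefined. Angiographic success, treatment failure, recurrence and the modality comparison are therefore open to selection on the outcome. Complication rates by modality share the problem of attributing outside treatments.

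Size and direction are unknown. The shift from 20% to between 23.8% and 33.3%, and the odds ratios of 1.38 to 1.75 between equally effective modalities, rest wholly on assumed failure rates and referral shares, and on all referred-in cases being failures coded under their first treatment. The structural finding rests only on the eligibility text and the variable list. It should be corrected before the treatment analyses are run, because without the field the investigators cannot measure the problem either.

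**What to change.** 1. Define initial treatment, in the protocol and the spreadsheet, as the first SDAVF treatment ever given, wherever it was given.
2. Add one drop-down field: *SDAVF treatment before first contact with this centre: none / yes, treated elsewhere / unknown*.
3. Run the primary analyses of angiographic success, treatment failure, recurrence, complications and the modality comparison in patients coded *none*. This keeps conservatively managed patients, and those first evaluated at the centre and treated elsewhere afterwards. A simple yes/no field on whether first treatment was given at the centre would lose or misclassify both groups.
4. Report the *yes* patients separately, for presentation and re-treatment outcomes.
5. Add a sensitivity analysis that includes the *yes* and *unknown* patients.

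The cost is one extra column, some re-checking of records already extracted before the end-of-February 2026 deadline in an unfunded study, and somewhat smaller denominators for the treatment analyses. The change does not recover in-house failures re-treated elsewhere without the centre's knowledge; that remains a limitation to report.

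### Patients with no baseline deficit on a scale are mixed into the functional comparisons across modalities, with no baseline restriction or adjustment set in the protocol

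*Protocol*

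**What the plan says.** Under Inclusion Criteria (Study Population), the protocol admits "Both symptomatic and incidental/asymptomatic cases". The exclusion criteria remove other lesion types and records too incomplete to confirm diagnosis or treatment. None refers to baseline deficit.

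Under Primary Outcomes, the functional endpoint is "Functional outcome at last follow-up as measured by mRS and Modified Aminoff–Logue scales". It is a final status, with no change score, cut-off or reference to baseline. The follow-up variables also include "Overall clinical status at last follow-up (improved, unchanged, worsened". A secondary objective is "To explore predictors of functional recovery using standardized outcome measures"; who counts as able to recover is not stated.

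The section headed Statistical Analysis Plan says: "Comparative analyses will be performed to evaluate outcomes across treatment modalities using appropriate statistical tests". Its examples are simple group tests such as chi-square and analysis of variance. On regression it says only: "Multivariable regression models may be used to identify independent predictors of outcomes and recurrence".

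The data to separate these patients are planned. Clinical History and Presentation lists "Incidental/asymptomatic presentation" and the presenting symptoms. The block "Functional Status at Diagnosis" lists gait, bladder and mRS.

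**The concern.** A scale has a best level, and a patient who starts there can only stay or get worse. This applies to a wholly asymptomatic patient and also scale by scale: a patient with gait loss and normal bladder function cannot improve on the bladder scale.

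If everyone is in the denominator, a patient who starts and stays free of deficit counts as not improved, yet also counts as a good final result. The two summaries move in opposite directions for a reason unrelated to treatment. Modalities are not randomised, so the share of such patients may differ between them. A modality with more of them would then look worse on improvement and better on final status with identical treatment effects. In a model for recovery, absence of deficit would appear as a predictor of non-recovery.

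**Working it through.** The protocol states no rate, cut-off, effect size or sample size, so there is no figure of its own to reproduce. The check is on direction and size, and every input below is an assumption.

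**Inputs**
- f: share of patients with no deficit on the scale at baseline
- p: improvement rate among patients with a deficit
- g: rate of good final status among patients with a deficit
- g0: rate of good final status among patients without one

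**Formulas**
- All-patient improvement = (1 − f) × p, a shift of −f × p
- All-patient good status = (1 − f) × g + f × g0, a shift of +f × (g0 − g)

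The shifts have opposite signs whenever g0 exceeds g.

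**Results (improvement / good status, %)**

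| f | p=50, g=40, g0=95 | p=60, g=50, g0=95 | p=40, g=30, g0=90 |
|---|---|---|---|
| 2% | 49.0 / 41.1 | 58.8 / 50.9 | 39.2 / 31.2 |
| 10% | 45.0 / 45.5 | 54.0 / 54.5 | 36.0 / 36.0 |
| 20% | 40.0 / 51.0 | 48.0 / 59.0 | 32.0 / 42.0 |
| 40% | 30.0 / 62.0 | 36.0 / 68.0 | 24.0 / 54.0 |

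At f = 2% the shift is about 1 point each way. At f = 20% it is −8 to −12 points for improvement and +9 to +12 points for good status. The 40% row is relevant to a single scale: if 40% have normal bladder function at baseline, a 50% improvement rate among those with a deficit is reported as 0.6 × 50% = 30%.

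**Comparison of two modalities with no true difference** (p = 50%, g = 40%, g0 = 95%)
- f = 5% versus 20%, improvement: 0.95 × 50% = 47.5% versus 0.80 × 50% = 40.0%, a false difference of −7.5 points.
- f = 5% versus 20%, good status: 0.95 × 40% + 0.05 × 95% = 42.75% versus 0.80 × 40% + 0.20 × 95% = 51.0%, a false difference of +8.25 points.
- With an assumed 200 patients per group and a two-sided 5% test of two proportions, these would be declared significant about 33% and 38% of the time. With 100 per group the figures are about 19% and 21%.
- With f = 5% versus 10% and 200 per group they are about 7% and 8%, close to the nominal 5%.

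Restricting to patients with a deficit returns p and g at every value of f.

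**The case against.** Several points on the other side stand.

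- A registry meant to characterise presentation properly includes incidental cases. In a description of final status for the whole cohort they count validly, and they can worsen.
- A reader might infer that the protocol puts these patients into the recovery analysis. It does not say so; the inference rests on the absence of any restriction. Recovery is an exploratory aim with no stated definition, no good-outcome rate is defined, and a separate analysis plan may set the denominator.
- A reader might infer that every incidental patient starts at mRS 0. The flag describes how the fistula presented. mRS measures overall disability, so such a patient can have a non-zero score from other disease. What matters is the baseline score on the scale, not the flag.
- A reader might infer that the symptom-evolution fields cannot record a symptom as absent at baseline. The protocol names those fields without listing their levels, and the spreadsheet is not shown. The three levels it does list belong to the overall-status item.
- The size is entirely assumed. A material bias between modalities needs a clear imbalance in f, for which the documents give no evidence.
- Limiting the primary comparison to patients with a deficit would drop those in whom a new treatment-related deficit is easiest to see. Baseline adjustment keeps them.

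These points narrow the concern but do not remove it. Eligibility, endpoint wording and data fields belong to the protocol, and its own statistical section pairs a final-status endpoint with unadjusted tests and leaves regression optional. The Data Sharing and Publication Policy also lets centers propose their own analyses, so recovery denominators could differ between papers without a common rule.

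**Conclusion.** The concern holds as a gap in how the functional comparisons are specified, not as an error in eligibility. Followed as written, the plan mixes patients who cannot improve on a scale into comparisons across non-randomised modalities without accounting for where they started. The direction follows from arithmetic, given only that patients without a deficit end well more often than those with one.

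The size depends on a share that the documents do not give. It is negligible at about 2% and material at 10% to 20% or more. On a single scale the share can exceed that of wholly asymptomatic patients. The change is worth making before analysis. The documents do not show that any reported rate is distorted, since none is defined.

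**What to change.** 1. Define recovery or improvement on mRS, gait and bladder among patients with a baseline deficit on the scale concerned, each with its own denominator.
2. Report patients with no deficit on that scale separately, as remained free of deficit or new deficit.
3. Keep all patients in the comparison of status at last follow-up, but adjust for the baseline score on the same scale. Add restriction to patients with a deficit as a sensitivity analysis.
4. Check that the spreadsheet's symptom-evolution fields and the overall-status item can record that nothing was present at baseline. If they cannot, derive this from the presenting-symptom fields.

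The cost is a few sentences in Outcomes and the statistical section, and somewhat smaller denominators per scale. The incidental flag and all three baseline scores are already collected, so items 1 to 3 need no new data. Any spreadsheet change under item 4 is best made before the data collection deadline at the end of February 2026.
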